1.1 Pharmacovigilance information

Pharmacovigilance data include any unintended or adverse event associated with the use of a medicinal product in humans, whether or not considered drug related, including the following special situations (situations where no adverse event occurred but information needs to be collected):

- exposure during pregnancy or breastfeeding;
- overdose, abuse, misuse, off-label uses, medication error, occupational exposure (including professional one);
- lack of the treatment efficacy of drug.

1.2. Adverse event (AE)

Adverse event (AE) is any untoward medical occurrence in a patient or clinical-trial participant who received the medicinal product, which does not necessarily have a causal relationship with the use of this medicinal product.

An adverse event can therefore be any unfavourable and unintended sign (e.g. an abnormal laboratory finding), symptom, or disease temporally associated with the use of a medicinal product, whether or not considered as related to the medicinal product.

1.3. Adverse (drug) reaction (ADR)

Adverse reaction (synonyms: Adverse drug reaction, Suspected adverse (drug) reaction, Adverse effect, Undesirable effect) is a response to a medicinal product which is noxious and unintended.

"Response" in this context means that a causal relationship between a medicinal product and an adverse event is at least a reasonable possibility.

Adverse reactions may arise from use of the product within or outside the terms of the marketing authorization or from occupational exposure. Conditions of use outside the marketing authorization include off-label use, overdose, misuse, abuse and medication errors.

1.4. Serious adverse (drug) reaction (SADR)

Serious adverse reaction is an adverse reaction, which results in death, is life-threatening, requires in-patient hospitalisation or prolongation of existing hospitalisation, results in persistent or significant disability or incapacity, or is a congenital anomaly/birth defect.

Life threatening in this context refers to a reaction in which the patient was at risk of death at the time of the reaction; it does not refer to a reaction that hypothetically might have caused death if more severe.

Medical and scientific judgement should be exercised in deciding whether other situations should be considered serious reactions, such as important medical events that might not be immediately life threatening or result in death or hospitalisation but might jeopardise the patient or might require intervention to prevent one of the other outcomes listed above. Examples of such events are intensive treatment in an emergency room or at home for allergic bronchospasm, blood dyscrasias or convulsions that do not result in hospitalisation or development of dependency or abuse.

Any suspected transmission via a medicinal product of an infectious agent is also considered a serious adverse reaction.

2. Responsibilities

2.1. Events to be reported

All available information about the following events reported during the study will be recorded:

- All serious adverse drug reactions related to the use of fixed-dose combination of amlodipine/ indapamide/ perindopril arginine
- All non-serious adverse drug reactions related to the use of fixed-dose combination of amlodipine/ indapamide/ perindopril arginine
- All reports about special situations (see 1.1)
- All adverse events.

2.2. Responsibilities of investigator

At medical visits during the program the investigator will ask a patient participating in the program to indicate whether or not an adverse event (serious or not) has occurred.

Investigator has to assess causal relationship between an adverse event and the investigated drug intake, as well as the seriousness criteria and later on the outcome of the event.

In case of Adverse Events, Adverse Drug Reactions or special situations that occurs during the program (both serious and non-serious), the investigator must complete the "Adverse event / Adverse drug reaction / Special Situation Reporting Form" (Appendix 1) without waiting for the clinical outcome or the results of additional investigations.

If the event is serious, it will be notified immediately (in the same or next working day at the latest) to Servier company in Russia via e-mail to address [contact] or by fax to number [name]. The anonymized copies of all the available and relevant laboratory findings, hospitalisation reports or other investigation results performed in connection with the adverse event should be attached to the form.

All other events should be reported by investigator within 2 working days.

The same rules apply for the transferring of additional information about the event.

The investigator must ensure the appropriate follow-up of the patient depending on the nature of event, until it resolves. The investigator will continue to notify follow up data according to timeframes defined above.

If investigator does not follow-up a patients anymore (i.e. in case of hospitalisation followed by the treatment by specialist or the participant's general practitioner,...), he/she will do every effort to contact the specialist or department in charge of follow-up of the patient, so as to have additional information and report it to Servier company in Russia.

2.3. Responsibilities of sponsor/marketing authorization holder (MAH)

Independently of the regulatory obligations of investigator, the sponsor/MAH must report the pharmacovigilance data to the appropriate authorities in accordance with the Good Vigilance Practice and local regulations.

Cases are closed when an adverse event has recovered or patient's condition was stabilized and the report is deemed sufficiently detailed for adequate medical analysis of the case.

Ethical considerations

The program will be conducted in accordance with the principles of the Declaration of Helsinki, as amended in Fortaleza, Brasil, in 2013. Protocol of program was checked and approved in accordance with the legislation of the Russian Federation and will be complied with by the sponsor, especially with regard to data protection. Patients will be fully informed, and they will need to provide a written consent before participation in the program. Investigator should confirm in the CRF that the patient has provided an informed consent. The "Informed consent" implies that there was an individual discussion with the participant about the nature of the interview and examinations to be conducted.

The sponsor will not have data that allow identification of participants.

The study documents will be approved by the Ethics Committee.

Organizational structure and responsibilities

Investigators will receive informed consent forms and involve participants, ensure data collection in accordance with the protocol, fill in case report forms (CRFs) and verify the accuracy of the information in these CRFs, as much as possible. The patient will be provided with all information to obtain informed consent. At the same time, participants will be asked to provide their consent to the use of their personal data. The data of the participants will remain completely confidential.

Sponsor

The sponsor will be responsible for all stages of the program, for providing the resources necessary to initiate and perform the program in accordance with local regulations, as well as for the validity of the recorded data.

Statistical center

All data will be transferred and centralized by the sponsor.

Effectiveness and tolerability variables:

- Mean change in the office SBP and DBP (in mm Hg) measured in the sitting position
- Percentage (%) of patients at the target levels of the office BP (SBP <140 mm Hg and DBP <90 mm Hg): in general sample and in subgroups (men, women, patients with IHD, diabetes, metabolic syndrome, ISAH, and patients older than 65 years)
- Change in the proportion of patients with different 24-hour BP profiles (dipper, non-dipper, reduced dipper, extreme dipper, nocturnal hypertension)
- Mean change in the 24-hour SBP and DBP (in mm Hg) in patients who performed ABPM
- Mean change in the daytime SBP and DBP (in mm Hg) in patients who performed ABPM
- Mean change in the nighttime SBP and DBP (in mm Hg) in patients who performed ABPM
- Percentage (%) of patients at the target levels of the office BP (24-hour SBP <135 mm Hg and DBP < 85 mm Hg) in patients who performed ABPM
- Change in the mean score of the SF-36 survey (Appendix 2)
- Changes in the treatment compliance score by the Compliance questionnaire (Appendix 3)
- List of SAEs
- List of AEs
- List of AEs that resulted in the withdrawal of the triple FDC of amlodipine / indapamide / perindopril arginine.
- List of ADR
- List of SADR
- List of special situations

Statistical parameters

All parameters will be analyzed using the methods of descriptive statistics. For each parameter, the number of patients, mean, standard error, minimum and maximum values will be indicated.

Statistical analysis

- The baseline characteristics will be analyzed in all the patients who started the treatment (intention-to-treat [ITT] population). In case of significant differences between two treatment groups, the baseline characteristics will be provided for both of them.
- Changes in the SBP and DBP (with the corresponding confidence intervals) will be assessed in the patients who completed the program without major deviations from protocol (per-protocol population [PPP]).
- The analysis of parameters with normal distribution will be performed using the Student's t-test for paired measurements; otherwise the non-parametric Wilcoxon test will be used. The percentage of patients with normalized BP, as well as the percentage of patients who responded to treatment (with 95% confidence intervals), will be calculated.
- Questionnaires: The score for each scale will be calculated as the sum of scores for questions constituting the scale.
- Assessment of the AEs will be carried out in all the patients who started the treatment (ITT population).

Administrative aspects

The ownership of documentation, data and results of the program.

The sponsor reserves the exclusive right to all materials, information, unpublished documentation, results and information received during the program. The sponsor reserves the right to send data from the program (case report forms, results of analysis, reports) to the health authorities.

No unpublished documentation or information transmitted to investigators can be transferred to unauthorized persons without the prior formal written permission of Sponsor.

Publication and communication

Sponsor is responsible for communication and publication of data on the program. No aspect of the results of this program or other data may be published, submitted or distributed without the expressed written permission of Sponsor. Participants of the program fully transfer to the Sponsor the authority for the first presentation, communication and publication of the results on behalf of all employees. No other communication or publication is permitted before this first publication. Any subsequent communication or publication must first be reviewed and approved by the Sponsor and must refer to the program and the first publication.

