At the same time, there are scarce data on several aspects of the use of triple FDCs. In particular, the advantages of triple FDCs in comparison with traditional approach to the treatment require complex investigation with the use of outpatient methods of BP measurement of. The effect of triple FDCs on the quality of life (QOL) of hypertensive patients is also of interest.

AIM AND OBJECTIVES OF THE PROGRAM:

To assess the antihypertensive effectiveness effect on the 24-hour BP profile, as well as tolerability of and compliance to the treatment with a triple FDC of amlodipine / indapamide / perindopril arginine in hypertensive patients in the real clinical practice.

Primary endpoints:

• The effectiveness of triple FDC of amlodipine / indapamide / perindopril arginine in terms of BP control in hypertensive patients from the real clinical practice.

Secondary endpoints:

- The 24-hour BP profile on the top of FDC of amlodipine / indapamide / perindopril arginine in hypertensive patients from the real clinical practice.
- Tolerability of the triple FDC of amlodipine / indapamide / perindopril arginine in hypertensive patients from the real clinical practice.
- Compliance with the treatment with triple FDC of amlodipine / indapamide / perindopril arginine in hypertensive patients from the real clinical practice.

DESIGN AND METHODOLOGY

Type of program: Multicenter, observational, non-controlled, open-label program. **Investigators:** Cardiologists and outpatient (primary care) physicians (general practitioners). **Number of patients:** 1,300 hypertensive patients.

The patient is included in the program if prior to the study his/her doctor decided to adjust treatment, targeted at the BP control improvement, by prescription of a triple FDC of amlodipine / indapamide / perindopril arginine. The prescription of the triple FDC of amlodipine / indapamide / perindopril arginine during the program is made by the doctor's decision according to the instructions for medical use of this FDC.

Presumably, each doctor will include 4 patients in average. It is planned to include 1,300 patients.

Time frame of the program

First subject in (FSI):	November, 2018
Last subject last visit (LSLV):	January, 2019
Database lock:	February, 2019
Statistic report:	May, 2019
Clinical study report:	January, 2020.

Inclusion criteria

- Age 18 to 79 years
- Essential hypertension
- Patient's consent to participate in the program

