- *BP self-monitoring*. Throughout the program, with the exception of the days scheduled for ABPM, patients will be keeping diaries of BP self-monitoring. The BP will be measured in a sitting position on the same arm of the working arm after a 5-minute rest with 1-2 minute interval between measurements. It is planned to carry out 3 measurements of BP in the morning after awakening (before breakfast and before taking the study drug) and in the evening before bedtime. In the diary, the average values of the SBP and DBP will be recorded, the BP will be monitored 6 days prior to the visit to doctor.
- Surveys:
 - Assessment of the *patient's quality of life (QoL)* will be carried out using the standardized QoL survey SF36 (Appendix 2).
 - Assessment of the *patient's compliance with the treatment* will be carried out using the compliance questionnaire (Appendix 3).
- Assessment of the treatment tolerability by completion of the standard pharmacovigilance form.

COURSE OF THE PROGRAM

The program will include hypertensive patients, to whom the doctor prescribed the triple FDC of amlodipine / indapamide / perindopril arginine in the routine clinical practice, based on his/her own experience and in accordance with the instruction for medical use of the drug.

Ambulatory Blood Pressure Monitoring [11]: The 24-hour BP profiles: *Dipper*: nighttime BP reduction >10% from daytime values, or ratio "nighttime/daytime BP» is <0.9 and >0.8 [normal 24-hour BP profile].

Reduced dipper: nighttime BP reduction by 1 to 10% from daytime values, or ratio "nighttime/daytime BP» is <1 and >0.9 [reduced 24-hour BP profile].

Non-dipper: Absence of nighttime BP reduction or its increase, or ratio "nighttime/daytime BP» is ≥ 1 [this profile is associated with a high cardiovascular risk].

Extreme dipper: The substantial nighttime BP reduction by >20% from daytime values or ratio "nighttime/daytime BP» is <0.8 [questionable cardiovascular risk].

Nocturnal hypertension: increase in the absolute values of nighttime BP.

Target BP level

In accordance with the guidelines of the Russian Hypertension Society (RMOAG)/Russian Society of Cardiology (VNOK) for the treatment of hypertension (2010, version 4), BP control is defined as office BP <140/90 mm Hg.

Duration of the program: 12 weeks.

During this time, the patient's visits to the doctor are scheduled in accordance with the presented flow chart.

•••				
Time	Week 0	Week 2	Week 4	Week 12
	(V1)	(V2)	(V3)	(V4)

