Defining the inclusion/non-inclusion	Х			
criteria	^			
Patient's informed consent	Х			
Medical history, risk factors and lifestyle	Х			
Recording of the current therapy	Х	Х	Х	Х
BP and HR measurements	Х	Х	Х	Х
Body weight and height	Х			
ABPM (in a part of patients)	Х			Х
Issuing the diaries for BP self-monitoring				
Recoding of the data of BP self-		Х	Х	Х
monitoring		^	^	^
Assessment of adverse events		Х	Х	Х
Completion of the QoL questionnaire	Х			Х
Completion of the Treatment compliance questionnaire	Х			X

Flow chart of the program

Visit 1 (inclusion in the program)

- Selection of patients; defining the inclusion/non-inclusion criteria.
- Providing a patient with the Diary for BP self-monitoring and instruction on its completion.
- Carrying out the following examinations:
 - o BP and HR measurements;
 - \circ $\;$ ABPM (in those patients, to whom it was prescribed by the doctor).
- Recoding of the current therapy; completion of the questionnaires:
 - SF36 questionnaire for the QoL assessment (Appendix 2);
 - Patient's treatment compliance questionnaire (Appendix 3).

Visit 2

- Carrying out the following examinations:
 - o BP and HR measurements;
 - Control of the completion of BP self-monitoring diary by a patient.
- Antihypertensive treatment at the time of visit.
- Assessment of the adverse events.

Visit 3

- Carrying out the following examinations:
 - o BP and HR measurements;
 - o Control of the completion of BP self-monitoring diary by a patient.
- Antihypertensive treatment at the time of visit.
- Assessment of the adverse events.

Visit 4. Completion of the program

- Carrying out the following examinations:
 - o BP and HR measurements;
 - \circ ABPM (in those patients, to whom it was prescribed by the doctor).
- Antihypertensive treatment at the time of visit.
- Completion of the questionnaires:
 - SF36 questionnaire for the QoL assessment (Appendix 2);
 - Patient's treatment compliance questionnaire (Appendix 3).
- Assessment of the adverse events.

• Collection of the diaries of BP self-monitoring.

CONCOMITANT TREATMENT

The treatment with any drugs, including antiplatelets, statins, nitrates, anti-inflammatory or other drugs, is determined by the treating physician.

Diet and physical activity

During the program there will be no additional restrictions of diet or physical activity.

Collecting and reporting the safety data

1. Definitions

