2. Role physical (RP)	4A, 4B, 4C, and 4D	3 – 8	4
3. Bodily pain (BP)	7 and 8	2 – 12	10
4. General health (GH)	1, 11A, 11B, 11C, and 11D	5 – 25	20
5. Vitality (VT)	9A, 9E, 9G, and 9I	4 – 24	20
6. Social functioning (SF)	6 and 10	2 – 10	8
7. Role emotional (RE)	5A, 5B, and 5C.	3 - 6	3
8. Mental health (MH)	9B, 9C, 9D, 9F, 9H.	5 – 30	25

For items 6, 9A, 9E, 9D, 9H, 10, and 11, the count-down is applied.

The formula for calculating the values:

[(actual value of the scale) – (minimal possible value on the scale] : (possible range of values) \Box 100.

Requirements for presenting the results:

- 1. Number of cases per each parameter should be indicated;
- 2. Descriptive statistics: M ± SD, Me (LQ; UQ), % (n/N);
- 3. Accuracy of results (estimates, P value); Confidence interval (for main results of the study) and P value;
- 4. Statistical methods (parametric and non-parametric) and statistical packages should be mentioned.

The recommended statistical packages for the data processing are StatSoft Statistica v.6.0, and SPSS 9.0.

Assessment of patient's compliance with medical therapy [12].

Question	YES	NO
Did you forget to take your medication this morning?		
Since the last visit to the doctor, have you run out of your medication?		
Have you ever taken your medication later than the usual time?		
Have you ever not taken your medication because, on some days, you forgot about it?		
Have you ever not take your medication because you had the impression that it was doing		
more harm than good?		
Do you think that you have too many tablets to take?		

Answer "No" to all the questions: good compliance;

Answer "Yes" to 1-2 questions: minor compliance;

Answer "Yes" to 3 or more questions: noncompliance.

References

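### Compliance with the triple FDC is reported only from a week 12 questionnaire that does not identify the FDC, so the result describes V4 attendees rather than all who started it

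*Combined protocol and SAP*

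**What the plan says.** The *Secondary endpoints* list includes "Compliance with the treatment with triple FDC of amlodipine / indapamide / perindopril arginine in hypertensive patients from the real clinical practice". The methods section says that the assessment "will be carried out using the compliance questionnaire (Appendix 3"); no pill count, refill record or measure of persistence is named.

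The *Flow chart of the program* places "Completion of the Treatment compliance questionnaire" at V1 (week 0) and V4 (week 12) only. The same chart has current therapy recorded at all four visits.

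Under *Effectiveness and tolerability variables*, the compliance variable is "Changes in the treatment compliance score by the Compliance questionnaire (Appendix 3"). The only planned output on stopping the drug is "List of AEs that resulted in the withdrawal of the triple FDC of amlodipine / indapamide / perindopril arginine". A list of special situations is also planned.

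The questionnaire has six yes/no items, on forgetting, running out, lateness, perceived harm and tablet burden. None names the FDC or asks whether it is still being taken. The first scoring line is "Answer 'No' to all the questions: good compliance". The other two categories depend on the number of Yes answers, and there is no category for a patient who has stopped the FDC.

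The *Statistical analysis* section assigns the ITT population to baseline characteristics and adverse events, and the per-protocol population to changes in SBP and DBP. It assigns none to compliance.

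**The concern.** The endpoint concerns one product, and the instrument asks about whatever the patient is taking. Under the plan as written, a patient who stops the FDC can go one of two ways. If the patient does not attend V4, there is no post-baseline form and no change score. If the patient attends V4 on a different regimen, the six items can all be answered No and the form reads as good compliance, although the patient is no longer on the FDC.

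Both routes favour the product when the figure is read as compliance among those who were started on it. A large sample does not help, since the problem is who is in the denominator and which drug the answers refer to. The data that would separate these patients are largely collected through the therapy record, but no planned variable uses them.

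**Working it through.** **Step 1: which administration measures the FDC.** *Design and methodology* says a patient enters if "prior to the study his/her doctor decided to adjust treatment, targeted at the BP control improvement, by prescription of a triple FDC". The V1 form therefore reflects treatment before the FDC. V2 and V3 have no form. V4 is the only measurement of compliance made after the FDC is started.

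**Step 2: who contributes.** A change score needs both V1 and V4, and the paired tests in *Statistical analysis* need complete pairs. Anyone without a V4 form drops out. The documents do not say whether a patient who stops the FDC stays in the program to V4.

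**Step 3: where stopping is visible.** Adverse events that led to withdrawal are listed. Section 1.1 makes lack of efficacy, misuse, medication error and pregnancy exposure reportable as special situations, so some other stops may appear in that list. They would appear as events. No output gives the number who stopped over the number who started.

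**Step 4: illustration of scale.** The plan states no compliance figure, so there is none to reproduce. The inputs are:

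- N = 1,300, from the protocol.
- d, the share of starters who stop the FDC by week 12. Not in the documents; assumed 5%, 10% and 20%.
- g, the share with good compliance among those still on the FDC at V4. Not in the documents; assumed 60%.

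For simplicity, everyone still on the FDC attends V4. The share of all starters on the FDC with good compliance is g(1 − d). If stoppers are missing, the reported figure is g, and the gap is g − g(1 − d) = g × d. If every stopper attends on another drug and scores good, the reported figure is g(1 − d) + d, and the gap is d.

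| d | Stoppers | g(1 − d) | Reported, stoppers missing | Gap | Reported, all stoppers score good | Gap |
|---|---|---|---|---|---|---|
| 5% | 65 | 0.60 × 0.95 = 57% | 60% | 3 | 57 + 5 = 62% | 5 |
| 10% | 130 | 0.60 × 0.90 = 54% | 60% | 6 | 54 + 10 = 64% | 10 |
| 20% | 260 | 0.60 × 0.80 = 48% | 60% | 12 | 48 + 20 = 68% | 20 |

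In a mixed case at d = 10%, half the stoppers attend on another drug and 60% of them score good. The reported figure is (0.54 + 0.05 × 0.60) / 0.95 = 0.57 / 0.95 = 60%, the same as if all were missing.

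Over a wider assumed range, g = 50–80% and d = 2–20%, the gap with stoppers missing runs from 0.50 × 0.02 = 1 point to 0.80 × 0.20 = 16 points.

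**Step 5: comparison with sampling error.** At g = 60% and d = 10%, the 95% half-width, treating patients as independent, is 1.96 × √(0.60 × 0.40 / 1,170) = 2.8 points. A 6-point gap would lie outside it.

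These figures concern the percentage in the good category. The documents give no score distribution, so the effect on the planned change score cannot be estimated.

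**The case against.** The strongest reply is that this is a gap of definition before it is bias. Adherence among patients with data and adherence multiplied by persistence are different quantities, and a descriptive secondary endpoint in an uncontrolled program may legitimately report the first. A doctor-directed switch is also not non-compliance in the ordinary sense. This stands in part: the first quantity is reportable, but it must be labelled as such, and the endpoint as worded does not limit it to patients still on the FDC.

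Patients who stop on their own may well answer Yes to the items on running out, forgetting or perceived harm. That stands. The all-good column above is an upper bound that is unlikely for them, and the mixed case shows that scoring on a replacement drug need not add to the gap.

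The plan requires the number of patients for each parameter, so missing forms would be partly visible. That also stands, but a count of forms does not show who had left the FDC.

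A reader might go further and infer that the plan counts switched patients as compliant with the FDC. The documents do not say so. They give no rule, and a per-protocol restriction, had one been applied to compliance, might have excluded such patients. A reader might also infer that stops without an adverse event enter no result at all. The list of special situations can capture some of them, though not as stops with a denominator.

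**Conclusion.** The point holds in a limited form. Followed as written, the plan yields a compliance result for V4 attendees, including any who are no longer on the FDC, and no figure for how many of those who started were still taking it. As a statement about all starters it is likely to be too favourable.

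The size is unknown. The 3–12 points rest on assumed stop rates of 5–20% and an assumed 60% with good compliance among those remaining. They describe the percentage in the good category and should not be read as an estimate of error in the planned change score.

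This is an improvement that should be made to a secondary endpoint. It does not affect the primary endpoint, and most of the information needed is already recorded.

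**What to change.** Amend *Effectiveness and tolerability variables* and *Statistical analysis* as follows:

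- **(a) FDC status.** From the recorded therapy, report the percentage of all who started treatment (ITT) who are on the FDC, off the FDC, or of unknown status at V2, V3 and V4. The unknown category is needed because a missed visit leaves no therapy record.
- **(b) Compliance categories.** Report the V4 categories with all starters as the denominator. Show FDC stopped and unknown/missing as separate categories, and do not count a patient who is off the FDC as having good FDC compliance. State in advance which of the two a patient falls into if recorded as off the FDC earlier and then absent at V4.
- **(c) Change in score.** Restrict it to patients still on the FDC at V4, and label it so.

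Report the reason for stopping only where it is already recorded, for example on adverse event or special-situation forms. The visit schedule shows no separate field for it.

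The cost is SAP wording and one more table from data already collected. The downside for the sponsor is a less favourable compliance figure.

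### The change in SBP and DBP is assigned to the per-protocol set, and no analysis of it is specified in all who started the triple FDC; as a secondary gap, the rate below 140/90 has no named set, time point or missing-reading rule

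*Combined protocol and SAP*

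**What the plan says.** The Statistical analysis section of the combined protocol and SAP defines two sets.

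- **All who started (ITT).** It is used twice: "The baseline characteristics will be analyzed in all the patients who started the treatment (intention-to-treat [ITT] population") and "Assessment of the AEs will be carried out in all the patients who started the treatment (ITT population").
- **Per-protocol (PPP).** Changes in SBP and DBP, with confidence intervals, "will be assessed in the patients who completed the program without major deviations from protocol (per-protocol population [PPP"). The supplied text does not define a major deviation.

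The test for change is a paired t-test or, failing normality, a Wilcoxon test. Both need two readings per patient.

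BP control is the primary endpoint (Primary endpoints), and Target BP level defines control as office BP below 140/90 mm Hg. Under Effectiveness and tolerability variables the percentage at target is to be given "in general sample and in subgroups". The analysis text adds that "The percentage of patients with normalized BP, as well as the percentage of patients who responded to treatment" will be calculated with 95% confidence intervals. Neither place names ITT or PPP, gives a time point, or says how a patient without a reading is counted.

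Statistical parameters applies descriptive statistics to every parameter: "For each parameter, the number of patients, mean, standard error, minimum and maximum values will be indicated". It names no set.

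**The concern.** With no comparator, any selection of patients passes straight into the mean change. Two kinds of patient drop out of the per-protocol mean. Early leavers have no week-12 reading. Completers with a deviation may have a week-12 reading that is then not used. The plan foresees the first kind, because it lists adverse events that led to withdrawal of the FDC. Such patients count in the safety assessment but not in the assigned analysis of BP change.

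The stated aim is effectiveness in real clinical practice. A mean over completers without major deviations answers a narrower question. It overstates the fall if those left out did worse, understates it if they did better, and is unbiased if they did equally well.

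For the control rate the problem is different: the denominator is unstated, so the headline percentage could be formed in more than one way after the data are seen. In an open-label, single-group program the BP data are visible before database lock.

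**Working it through.** **No plan figure to reproduce.** The plan gives 1,300 patients without a derivation, and states no exclusion rate, SD, expected control rate or intraclass correlation (ICC). From the documents: N = 1,300 and an average of 4 patients per doctor (Design and methodology). Everything else is assumed and shown as a range.

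**1. Bias in mean change.** Let F be the per-protocol fall, d the share of starters left out, and F − delta their fall.

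All-starter fall = (1 − d)F + d(F − delta) = F − d × delta, so bias = d × delta.

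| delta (mm Hg) | d = 5% | 10% | 15% | 20% |
|---|---|---|---|---|
| −5 | −0.25 | −0.50 | −0.75 | −1.00 |
| 0 | 0 | 0 | 0 | 0 |
| 5 | 0.25 | 0.50 | 0.75 | 1.00 |
| 10 | 0.50 | 1.00 | 1.50 | 2.00 |

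**2. Precision as a yardstick.** Half-width = 1.96 × SD / √n, with n = 1,300 × (1 − d) = 1,235, 1,170, 1,105 and 1,040.

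| SD (mm Hg) | d = 5% | 10% | 15% | 20% |
|---|---|---|---|---|
| 12 | 0.67 | 0.69 | 0.71 | 0.73 |
| 15 | 0.84 | 0.86 | 0.88 | 0.91 |
| 18 | 1.00 | 1.03 | 1.06 | 1.09 |

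Clustering by doctor: design effect = 1 + (4 − 1) × ICC, which is 1.15 at ICC 0.05 and 1.30 at ICC 0.10. The half-width is multiplied by √1.15 = 1.072 or √1.30 = 1.140. At d = 10% it becomes 0.74 to 0.78 (SD 12), 0.92 to 0.98 (SD 15) and 1.11 to 1.18 (SD 18).

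**3. Comparison at d = 10%.**

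- delta = 5: bias 0.5, below every half-width.
- delta = 10: bias 1.0, above the half-width at SD 12 and 15 (with or without clustering), below it at SD 18.
- Break-even |delta| = half-width / d = 6.9, 8.6 and 10.3 mm Hg at SD 12, 15 and 18 without clustering; 7.8, 9.8 and 11.8 at ICC 0.10.

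Over the whole grid (4 values of d, 4 of delta, 3 of SD) the absolute bias exceeds the half-width in 14 of 48 cells, and in 10 of 48 at ICC 0.10. The half-width measures precision, not clinical importance.

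**4. Control rate.** Let p be the observed rate among those with a reading and m the share without one. Counting missing as not controlled gives p(1 − m), so the gap is m × p.

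| p | m = 5% | 10% | 15% | 20% |
|---|---|---|---|---|
| 60% | 3 | 6 | 9 | 12 |
| 70% | 3.5 | 7 | 10.5 | 14 |
| 80% | 4 | 8 | 12 | 16 |

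Entries are percentage points. At p = 80% and m = 10% (n = 1,170) the 95% half-width is 1.96 × √(0.8 × 0.2 / 1,170) = 2.3 points, against a gap of 8. The gap shows how far the figure can move under an unstated rule. It does not estimate bias.

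**The case against.** **The plan does not rule out an all-starter summary.** The general descriptive sentence covers every parameter and carries no per-protocol restriction. This stands in part: such a summary is unspecified, not excluded. But the sentence names no set, so it promises none, and the only set named for BP change is per-protocol.

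**The primary endpoint is control, not mean change.** True. A reader might infer that the primary endpoint is analysed in completers only; the documents do not say that. The phrase about the general sample contrasts with the subgroups and maps to neither set. This is an unstated denominator, and by itself mostly missing detail.

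**Other outputs help.** The number of patients per parameter, and the n/N format in the presentation requirements of Appendix 2, would show the denominator, but only afterwards. Adverse events leading to FDC withdrawal are listed. The "List of special situations" covers "lack of the treatment efficacy of drug" (section 1.1). These identify cases but do not give the BP change of those left out.

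**The size is assumed.** This stands. Most cells of the grid fall below the half-width, and the direction is unknown.

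**A repeated-measures model goes beyond the need** in a descriptive single-group program. This also stands, and the model is only optional below.

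**Conclusion.** The point holds and should be fixed, with moderate confidence. The text assigns BP change to the per-protocol set and specifies no all-starter analysis, which does not match a real-practice aim in a program without a control group. The unspecified control-rate denominator is a related but lesser gap.

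The size cannot be fixed from the documents. On assumed inputs with 10% left out, the bias ranges from −0.5 mm Hg (delta = −5) to 1.0 mm Hg (delta = 10), against half-widths of 0.69 to 1.03 without clustering.

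Two stronger readings are not supported. A reader might infer that the plan overstates the drug's effect; the bias can have either sign, and nothing in the documents fixes it. A reader might also infer that the per-protocol set contains only patients who took their treatment well. The supplied text does not define major deviations, does not make poor compliance one, and measures compliance as an outcome. The absence of a definition can be claimed only for the supplied text, since part of the document was removed before review.

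**What to change.** 1. **Main set.** Use all patients who started the FDC and have a V1 office BP for both BP change and BP control. Keep the per-protocol set as supportive.
2. **BP change.** Report the planned paired test in everyone with V1 and V4 readings, with or without a deviation. Show early leavers' available readings by visit. A repeated-measures model on V1 to V4 (weeks 0, 2, 4 and 12), valid under missing at random, is optional.
3. **Readings after FDC withdrawal.** State in advance whether they are included.
4. **BP control.** State the time point; week 12 (V4) is an inference from the flow chart. In the same set, report the observed rate below 140/90 and the rate with missing readings counted as not controlled.
5. **Deviations.** List the major deviations before the BP data are reviewed, and report per-protocol exclusions by reason.

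The cost is SAP wording and modest extra analysis of readings already scheduled; no new data are needed. The downside is a possibly less favourable headline figure and two control figures instead of one. The paired test still says nothing about early leavers at week 12, and the optional model would not protect against dropout that depends on unobserved BP.
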